3.2 Number of Centers

There have been 80 cases enrolled to date in the prospective arm of the study at seven study centers. The number of centers will be determined by the number of cases that are screened successfully into the retrospective cohort of this amendment.

3.3 Number of Subjects

Prospective enrollment will close with this protocol amendment at 80 cases. The last case was enrolled on January 29, 2018. Retrospective enrollment will be initiated at current study centers who have subjects that meet the enrollment criteria. The number of subjects obtained retrospectively will be a minimum of 95 cases from those implanted by the surgeon prior to the initiation of this study and any cases done after the original enrollment goal was met. If there are insufficient cases at the existing sites, other sites will be considered. These cases will have the Triathlon® PKR Unicompartmental Knee System. A total of 175 cases (knees) will be enrolled, 80 cases from the prospective cohort and a planned minimum of 95 cases from the retrospective cohort.

3.4 Estimated Study Duration

The enrollment period for the retrospective arm is estimated at six months to identify, screen and enroll all the retrospective cases, once IRB approval has been granted. All cases will be followed through 10 years postoperative.

4 Eligibility

The following criteria will be used to distinguish subjects eligible for enrollment into this study.

4.1 Inclusion Criteria

- 1) The subject is a male or non-pregnant female 21-75 years of age at the time of enrollment.
- 2) The subject requires a primary cemented unicompartmental knee replacement.
- 3) The subject has a diagnosis of osteoarthritis (OA) or post-traumatic arthritis (TA).
- 4) The subject has clinically intact cruciate and collateral ligaments and no ligamentous instability is present.
- 5) The subject has less than 10 degrees of flexion contracture and greater than 90 degrees of flexion.
- 6) The subject's preoperative mechanical alignment is less than 15 degrees of varus and 15 degrees of valgus.
- 7) The subject has signed the IRB approved study specific Informed Patient Consent Form.
- 8) The subject is willing and able to comply with postoperative scheduled clinical and radiographic evaluations and rehabilitation.

4.2 Exclusion Criteria

- 1) The subject has inflammatory arthritis or avascular necrosis (AVN).
- 2) The subject is obese, BMI >35.
- 3) The subject has a history of total or unicompartmental (contralateral compartment and/or patellofemoral joint) reconstruction of the affected joint.
- 4) The subject has a history of ACL reconstruction.
- 5) The subject has had a high distal femoral, or proximal tibial osteotomy.
- 6) The subject has a mental, neuromuscular or neurosensory disorder, which would create an unacceptable risk of prosthesis instability, prosthesis fixation failure, or complications in post-operative care and/or limit the ability to assess the performance of the device.

- 7) The subject has a systemic or metabolic disorder leading to progressive bone deterioration that the surgeon feels would affect the overall outcome of the study.
- 8) The subject is immunologically suppressed or is receiving chronic steroids (>30 days duration).
- 9) The subject has a known sensitivity to device materials.
- 10) The subject's bone stock is compromised by disease and/or infection which cannot provide adequate support and/or fixation to the prosthesis.
- 11) The subject's bone stock is compromised by a prior implantation which cannot provide adequate support and/or fixation to the prosthesis.
- 12) The subject has an active or suspected latent infection in or about the knee joint.
- 13) The subject is a prisoner.

5 Subject Enrollment

5.1 Treatment Assignment

All subjects enrolled in this study will have the Triathlon® PKR Unicompartmental Knee System. See **Appendix A** for Component Listing.

5.2 Randomization

This study will enroll under a non-randomized study design.

6 Device Description

6.1 Study Device

The Triathlon[®] Partial Knee Resurfacing (PKR) System has been cleared for use in the U.S. and is therefore considered a post market assessment under 510(k) clearance number K071881. See **Appendix B** for the FDA clearance letters. The Triathlon[®] PKR System consists of the following three primary components listed with this 510(k)clearance number: Triathlon[®] PKR Femoral Component (K071881), Triathlon[®] PKR Tibial Insert (K071881) and Triathlon[®] PKR Tibial Tray CONFIDENTIAL

This material is the property of Stryker. Do not disclose or use except as authorized in writing by Stryker.

(K071881). The Triathlon® PKR (Partial Knee Resurfacing) System consists of sterile, single-use components intended for replacement of the femorotibial regions of the knee joint either on the lateral or medial side. The system includes a femoral component and a modular tibial tray with a mating tibial insert. The system is intended for cemented fixation. The articular surface of the Triathlon® PKR insert is designed to allow the following kinematics: Range of Motion 0° hyperextension to 135° flexion.

The Triathlon® PKR (Partial Knee Resurfacing) System labeling can be found in Appendix C.

FEMORAL COMPONENT:

The Triathlon® PKR femoral component was designed with the same philosophy and rationale as the Triathlon® Total Knee System to have a single radius to recreate the natural movement of the epicondyle and to promote deep flexion. It is available in sizes ranging from Size 1 to Size 6 in right lateral/left medial and left lateral/right medial configurations. The component is fabricated from cast CoCrMo alloy and has two fixation pegs. The bone/cement facing surface of the component is grit blasted and the articulating surface is highly polished.

The Triathlon® PKR femoral component included in this protocol is:

5610-F-xxx

TIBIAL TRAY:

The Triathlon® PKR tibial component is cast cobalt chromium alloy. There are six sizes (1, 2, 3, 4, 5, and 6) in left medial/right lateral and right medial/left lateral configurations. The underside of the tibial component contains a cement recess, a round peg and an angled peg for cement fixation and to provide stability. The inside of the tray has tabs and lip for locking the tibial insert in place. The surface finish of the underside of baseplate is grit blasted and the topside is bead blasted.

The Triathlon® PKR tibial tray included in this protocol is:

• 5620-B-xxx

TIBIAL INSERT:

The tibial insert is fabricated from Ultra High Molecular Weight Polyethylene (UHMWPE) and is available in six sizes with thicknesses of 8mm, 9mm, 10mm and 12mm for the left medial/right

lateral and right medial/left lateral compartments. The articulating surface of the insert is based on the EIUS tibial insert cleared in K992287 and K033769. The locking mechanism between the insert and the tibial tray is based on the SCR® tibial insert design cleared in 510(k) K896856 and K911373. The tibial insert has undercuts on the bottom. When the insert slides under the lip on the tray, it snap-fits into place and the metal tabs on the tray mechanically lock the insert in place via the undercuts on the bottom of the insert. The minimum thickness of the thinnest tibial insert under the bearing surface meets the 6mm minimum noted by FDA guidance.

X3[®] polyethylene is a highly cross-linked polyethylene manufactured through a proprietary process where the polyethylene receives 30 kiloGrays of gamma radiation, which generates free radicals and cross-linking in UHMWPE prior to machining. The polyethylene is then annealed below melting point to promote cross-linking and maintains mechanical strength¹, crystallinity², and density³. This also stabilizes the free radicals⁴. This process is repeated twice.

The Triathlon® PKR tibial insert included in this protocol is:

• 5630-G-xxx

6.2 Device Retrieval Process

Stryker Orthopaedics will retrieve any Triathlon[®] PKR System components and/or adjacent tissues for analysis to help characterize potential device-related complications. In the event that any portion of the Triathlon[®] PKR system is removed from a study subject, please follow the procedure outlined below.

.

¹ X3 UHMWPE maintains mechanical properties for Tensile Yield Strength and Ultimate Tensile Strength of N_2 Vac gamma sterilized UHMWPE as measured by ASTM D638. Tensile Yield Strength was 23.2 ± 0.4 MPa and 23.5 ± 0.3 MPa for N_2 Vac UHMWPE and X3 UHMWPE, respectively. Ultimate Tensile Strength was 54.8 ± 2.5 MPa and 56.7 ± 2.1 MPa for N_2 Vac UHMWPE and X3 UHMWPE, respectively.

² X3 UHMWPE has similar crystalline and lamellar structure as N_2 Vac gamma sterilized UHMWPE as measured by Small Angle X-ray Scattering (SAXS) and Differential Scanning Calorimetry (DSC) analysis. DSC determined crystallinity was $61.3 \pm 0.8\%$ and $61.7 \pm 0.6\%$ for N_2 Vac UHMWPE and X3 UHMWPE, respectively. Lamellar crystal thickness was 23.0 and 23.6 nanometers for N_2 Vac UHMWPE and X3 UHMWPE, respectively.

³ X3 UHMWPE increases crosslink density over N_2 Vac gamma sterilized UHMWPE by 87% as measured by swell ratio per ASTM F2214. Crosslink density as measured by swell ratio was 0.08 ± 0.00 mol/dl and 0.15 ± 0.01 mol/dl for N_2 Vac UHMWPE and X3 UHMWPE. respectively.

⁴ X3 UHMWPE virtually eliminates free radicals, as measured by Electron Spin Resonance (ESR). A very low (noise level, near instrument detection limit) concentration of residual free radicals was detected in the X-3 UHMWPE. A 99% reduction of free radicals ($14 \pm 2 \times 10^{14}$ spins/gram versus $1550 \pm 32 \times 10^{14}$ spins/gram) was found when compared to N₂Vac gamma sterilized UHMWPE.

- 1. When revision of a study subject is scheduled, the study coordinator (SC) should complete a Product Experience Report (PER) and contact the CSM as soon as possible.
- 2. After contacting the CSM, the SC will fax the PER to the clinical study manager (CSM).
- 3. The CSM will obtain a PER number and relay the number to the SC.
- 4. The CSM will send an Exakt-Pak with corresponding PER label to the Field Representative for the site.
- 5. The field representative will retrieve the device, place it in the Exakt-Pak with the corresponding label and send to the CSM.
- 6. The CSM will then take the retrieval to Product Surveillance for analysis.
- 7. A summary of results will be provided to the investigator upon his/her request.

7 Evaluations

7.1 Initial Retrospective Evaluation

Once the subject has been screened and confirmed that they meet all inclusion and exclusion criteria, the subject will be consented. A medical record review will commence to obtain baseline information. The subject will be scheduled for the next annual follow-up that they are due for based on the original surgery date and as per the Evaluation Schedule on page 4. The earliest visit accepted will be five years postoperative, which means subjects will have to have a surgery date of 2015 or earlier. The initial medical record review will include obtaining: demographic/medical history, surgical details, a baseline evaluation at either two weeks, six weeks or three months and Knee Society Score elements; pain level and range of motion values. The anteroposterior (AP, standard and long-standing), mediolateral and merchant/skyline x-rays are optional. The AP long-standing film will only be used as a reference to determine if the subject meets the protocol inclusion of not having a preoperative varus or valgus deformity of greater than 15 degrees.

For the initial retrospective cases, as much of the preoperative data and baseline data will be retrospectively collected from the medical records upon completion of written consent. The patient reported outcomes (SF-12, LEAS, Activity Questionnaire and KOOS) will not be available prior to consent but will be collected from the point of consent forward to ten years.

7.2 Surgery

Surgical details will be collected from the operative notes and at the time of surgery. For the retrospective arm of the study, as much of the surgical details data will be collected from the operative notes and medical records. Information collected on the surgical details includes items such as: type of anesthesia, surgical approach, incision length, navigation use, bone removal, soft tissue released, ACL status, component catalog and serial number, blood loss, duration of surgery, and Outerbridge Classification.

Because this is a unicompartmental knee system, it is important to gauge the degree of disease in the contralateral compartment and patellofemoral compartment of the knee at the time a unicondylar knee replacement is being considered. Therefore, the Outerbridge Classification⁶ will be used in this study to assess the contralateral compartment and patellofemoral compartment in the knee joint. This classification system uses a grading system from Grade 0 to Grade IV to indicate the quality of the cartilage in each portion of the knee joint.

The Outerbridge Classification is as follows:

Grade 0: Normal cartilage

Grade I: Cartilage with softening and swelling

Grade II: fragmentation and fissuring in an area half an inch or less in diameter

Grade III: fragmentation and fissuring in an area more than half an inch in diameter

Grade IV: Erosion of cartilage down to bone

7.3 Annual Follow up Visits

[figure not shown]
Prospective cases will follow the original protocol for the postoperative visits. The retrospective cases enrolled under this amendment will be evaluated at 5, 7, and 10 years postoperatively, depending on the surgical date at the time of enrollment. At each office visit the following evaluations will be collected: Knee Society Score, SF-12, LEAS, Activity Questionnaire, KOOS. The anteroposterior (standard), mediolateral and merchant/skyline x-rays are optional.

8 Adverse Events

8.1 Adverse Event (AE) Reporting Requirements for this study

- All adverse events that meet the definition of serious (not to include elective surgeries)
- All AE's related to operative site, regardless of seriousness

See Adverse Event Decision Tree - Figure 1

Adverse Event Reporting Period

The study period during which adverse events must be reported is normally defined as the period from the initiation of any study procedures to the end of the study treatment follow-up. In other words, the start of study procedures is considered to be the point of consent. Therefore, any adverse events which fit the protocol defined reportable events must be reported from the time of obtaining consent throughout the study duration.

At each contact with the subject, the investigator must seek information on adverse events by specific questioning and, as appropriate, by examination. Information on protocol defined adverse events should be recorded immediately in the source document, and also in the appropriate adverse event module of the case report form (CRF). All clearly related signs, symptoms, and abnormal diagnostic procedure results should be recorded in the source document, though they should be grouped under one diagnosis. The clinical course of each event should be followed until resolution or until it is determined at the end of the study that the adverse event will not resolve.

During the medical record review of the retrospectively enrolled cases, any operative site adverse events will be documented as per the usual procedure. For prospective follow-up, these cases will adhere to the adverse event reporting described above.

General Physical Examination Findings

At screening for inclusion into the study, any clinically significant abnormality should be recorded as a preexisting condition. During the study, any new clinically significant findings/abnormalities that meet the definition of a protocol defined adverse event must also be recorded and documented as an adverse event.

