	Primary Hypothesis: The mean KSS Function score is non-inferior to 84 points with a margin of 6 points. (Ha: u - 84>-6). The reference value 84 is from the Triathlon CR 10-year KSS Function value. The reference value of 6 is the minimal clinically important difference (MCID) per reference.
Statistical Methodology	Secondary Hypotheses: The 90% confidence interval of the success rate will be computed at 10-year post-surgery. For the non-inferiority comparison, the lower bound of this 90% confidence interval will be compared with 80%. For the superiority comparison, the lower bound of this 90% confidence interval will be compared with 88%.

Evaluation Schedule

CASE REPORT FORMS										
EVALUATION	HISTORY / PREOP (-3 mnths)	INTRA- OP	2 WKS (± 1 wk)	6 WKS (± 1 wk)	3 Months (± 2 wks)	1YR. (± 2 mos)	2 YRS. (± 2 mos)	5 YRS. (± 3 mos)	7 YRS. (± 3 mos)	10 YRS. (±3 mos)
Inclusion/ Exclusion	х									
Demographics /Medical History	Х									
Surgical Details		Х								
PRE Operative Evaluation/KSS	Х									
POST Operative Evaluation/KSS			х	х	Х	Х	х	х	х	х
SF-12	Х		Х	Х	Х	Х	Х	Х	Х	Х
Activity Questionnaire	Х		Х	Х	Х	Х	Х	Х	Х	Х
LEAS	Х		Х	Х	Х	Х	Х	Х	Х	Х
KOOS	Х		Х	Х	Х	X	Х	X	Х	Х
	RADIOGRAPHS**									
	PREOP (-1 year)	INTRA- OP	2 WKS (± 1 wk)	6 WKS (± 1 wk)	3 Months (± 2 wks)	1YR. (± 2 mos)	2 YRS. (± 2 mos)	5 YRS. (± 3 mos)	7 YRS. (± 3 mos	10 YRS. (±3 mos)
AP long standing	Х			Х						
AP standard	X			×		x	X	X	Х	X
ML standard	Х			Х		Х	Х	Х	Х	Х
Merchant/ skyline	Х			х		х	Х	Х	Х	Х

^{*}Cases enrolled in the retrospective cohort will have preoperative, postoperative and one postoperative baseline visit (either 2 wks., 6 wks. or 3 months) documented from the medical records. The earliest prospective visit is 5-years postoperative, therefore, the earliest surgical date for this retrospective cohort is 2015.

^{**}For the retrospective study cohort, the x-rays will be optional.

1 Introduction

This document is a protocol for a human research study. This study will be conducted in compliance with the protocol, Good Clinical Practice Standards, associated Federal regulations, and all applicable research requirements.

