2.2 Safety

Reported protocol defined adverse events will be compared to literature. It is expected that the adverse event rates reported for the Triathlon® PKR Unicompartmental Knee System will be comparable to those reported in the literature.

3 Clinical Study Plan

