9.2 Safety

9.2.1 Safety Parameters

Safety parameters include all protocol defined adverse events reported.

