9.2.2 Safety Analysis

All adverse events will be listed, tabulated, and summarized by event, number, and percent of cases/patients. Adverse event rates and exact 95% confidence intervals will be presented.

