6) How much d No limitation 7) How severe	0 1 was your kn	2 3 ee pain during	3 4 1 the performe	5 6	7	8	9 10		Limitation	
No pain	0 1	2 3	3 4	5 6		8		0 Severe	Pain	
Patient, please	initial and c	late here:			For Stryke Stamp Date			JDATE: ceipt		
DATE:	7/[/					Verifica Verifica	intry		

Stryker®	Triathion PKR Ou ADVERSE	Page 1 of 2			
[name]	PATIENT ID: 6 6 Study # Site # Subject #				
GENERAL INFORMATION PATIENT INITIALS: (If there is no middle initial please use "-")		DATE OF EVE	NT:/	YYY	
OPERATIVE SIDE: O Right O Le	eft (Check One)				
I. DESCRIPTION					
	Check one event in S	ection A or Se	ection B)		
Deep Joint Infection Excessive Knee Pain Femoral Fracture Loosening Femoral Component Loosening Patellar Component Loosening Tibial Component Myositis Ossificans	atellar Fracture atellar Subluxation atellar Tendon Rupture eroneal Nerve Palsy rosthesis Fracture / Fem rosthesis Fracture / Pate rosthesis Fracture / Tibia rosthesis Fracture / Tibia effex Sympathetic Dystro	llar Component Il Component Il Insert Ophy (RSD) Genitou Neurose Pulmona O Thrombe	Soft Tissue Trauma Superficial Wound Infection Supracondylar Fracture Tibial Component Subsidence Tibial Fracture Wound Hematoma Wound Related (Specify) Other (Specify) ensory (Specify) ary Embolism ophlebitis (Specify)		
Gastrointestinal (Specify) C. WHEN DID THE EVENT OCCUR? (Check on	۹۱	Other (Specify)			
O Pre-Op O Intra-Op O Post-Op	,				
II. COMPLICATION / CONCURRENT MEDICAL E D. HISTORY OR CAUSATIVE EVENT? Yes No	VENT (If Yes, specify signs,	symptoms and o	diseases.)		
E. DEVICE RELATED? (Check one) Yes No Uncertain	(If Yes or Uncertain, ex	xplain, complete	PER form and fax all pages to Stryker w	ithin 24 hours).	
F. SERIOUSNESS Does this event meet the def ☐ Resulted in inpatient hospitalization ☐ Resulted in prolonged existing hospitalization		preclude	medical or surgical intervention to permanent impairment of a body functionent damage to a body structure	n	
☐ Resulted in persistent or significant disabili	ty/incapacity	☐ Was a life threatening situation			
☐ Resulted in permanent impairment of a bod or permanent damage to a body structure	y function	☐ Resulted in patient death ☐ None of the above			
			all pages to Stryker within 24 hour licable source documentation.	S.	

Stryker® ADVERSE	### Page 2 of 2 EVENT PATIENT ID: 6 6 Study # Site # Subject #
GENERAL INFORMATION PATIENT INITIALS: (If there is no middle initial please use "-")	DATE OF EVENT:

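### Adverse event rates run from consent, so pre-implant events of prospective cases would count in rates compared with literature on events after UKA; the effect is probably small and the fix is one sentence

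*Combined protocol and SAP*

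**What the plan says.** Section 8.1 makes two kinds of event reportable: serious events (elective surgery aside) and any event at the operative site. It treats consent as the start of study procedures, so that "any adverse events which fit the protocol defined reportable events must be reported from the time of obtaining consent throughout the study duration".

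For prospective cases, consent comes before the operation. Section 4.1 lists as an inclusion criterion that "The subject has signed the IRB approved study specific Informed Patient Consent Form", and the Evaluation Schedule puts the inclusion/exclusion check in the column headed "HISTORY / PREOP (-3 mnths". Retrospective cases consent years after surgery. Section 8.1 has their operative-site events taken from the medical record.

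Item C of the adverse event form in Appendix E asks "WHEN DID THE EVENT OCCUR" and offers Pre-Op, Intra-Op and Post-Op.

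On analysis, section 9.2.1 says "Safety parameters include all protocol defined adverse events reported". Section 9.2.2 adds "All adverse events will be listed, tabulated, and summarized by event, number, and percent of cases/patients" and "Adverse event rates and exact 95% confidence intervals will be presented". Section 9.4.4 limits the safety population to non-censored subjects who received the device, and 9.4.5 takes out cases with an outcome-relevant deviation.

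On use, section 2.2 says "Reported protocol defined adverse events will be compared to literature". Section 12.3 supplies UKA literature rates (Table I) and, for total knees, literature rates and sponsor-study rates (Table II).

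**The concern.** An event between consent and surgery cannot have been caused by the implant or the operation. It belongs to the background of a patient waiting for surgery. Table I describes events during and after UKA. If the study's rates also carry events from the waiting period, they are raised relative to that literature for a reason unrelated to the device.

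The filters in 9.4.4 and 9.4.5 act on subjects, not on event dates. A subject with a serious event after consent who is later implanted stays in the safety population with that event. Item C would identify it, but no analysis rule uses item C.

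The consent-based window also gives a preoperative period to prospective cases only, so a pooled rate covers two different windows.

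**Working it through.** The plan states no figure that depends on this rule, so there is none to reproduce. The check follows one event through the sections and then bounds the exposure.

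**Path of an event in a prospective subject, after consent and before surgery**

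1. It is serious or at the operative site, so it is reportable (8.1).
2. It is recorded with item C = Pre-Op (Appendix E).
3. It is a reported protocol-defined event, so it is a safety parameter (9.2.1).
4. The subject is later implanted and not censored, so stays in the safety population (9.4.4, 9.4.5).
5. It is counted in the percentage and the exact interval (9.2.2), and the rate goes to the literature comparison (2.2, 12.3).

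No step removes it.

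**Inputs**

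- Prospective cases: 80; planned total: 175 (section 3.3).
- Preoperative visit window: 3 months = 0.25 year (Evaluation Schedule). The documents set no limit on the time from consent to surgery, so using this window as the maximum wait is an assumption.
- Follow-up: 10 years per case (Study Synopsis).

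**Exposure bound**

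- Pre-implant exposure: 80 x 0.25 = 20 case-years at most.
- Share of prospective observation: 20 / (20 + 80 x 10) = 20/820 = 2.4%.
- Share of all observation, every case counted over 10 years: 20 / (20 + 175 x 10) = 20/1770 = 1.1%.

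**Effect of one affected case on a crude rate**

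- Over 175 cases: 1/175 = 0.57 points.
- Over the 80 prospective cases: 1/80 = 1.25 points.
- Exact 95% interval over 175 cases: 0 to 2.1% with no event, 0.01% to 3.1% with one, 0.14% to 4.1% with two.

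**Expected number of events**

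The documents give no preoperative event rate. The rates below are assumptions for serious events of every kind together, at the full 20 case-years.

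| Assumed serious events per person-year | Expected events | Percent of 175 |
|---|---|---|
| 0.02 | 20 x 0.02 = 0.4 | 0.2% |
| 0.05 | 20 x 0.05 = 1.0 | 0.6% |
| 0.10 | 20 x 0.10 = 2.0 | 1.1% |
| 0.20 | 20 x 0.20 = 4.0 | 2.3% |

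A one-month wait would divide the expected counts by three. The totals are spread over many event rows, so they must not be set against a single row of Table I or II.

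**Rows that can be affected**

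- Implant-related rows cannot be: no implant was present.
- The death row cannot be: a subject who died before surgery was never implanted.
- Many systemic rows of Table I have no literature rate, among them bronchopulmonary, gastrointestinal, genitourinary and pulmonary embolism. Nothing is compared there.
- Rows with a Table I figure that a preoperative event could enter include excessive knee pain (0.2% to 5.5%), cardiovascular (8%), DVT (1% to 4%) and other systemic (3% to 8%).

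**The case against.** The strongest reply is that the gap has little consequence. At most about 20 case-years are involved, some 1% of all observation, and there is no formal safety test or threshold to cross. Section 9.2.2 already requires every event to be listed, and item C lets anyone separate the preoperative ones. Section 8.1 records abnormalities found at screening as preexisting conditions, and section 8.2 requires an adverse event to change the subject's medical baseline, so continuing pain in the arthritic knee would not by itself qualify. Other differences between the cohorts are larger. Before consent, retrospective cases contribute only operative-site events from the chart, and section 10.1 screens out patients who have died or been revised.

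Most of this stands, and it limits the size of the point. It does not remove the rule: the plan says that all reported events enter the rates, and the ability to separate them later is not a decision to do so.

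A reader might infer more than the documents support:

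- *That the rates are biased upward against the sponsor's total-knee studies.* This is not shown. Section 12.3 does not state the event window behind that column of Table II. If those studies also counted from consent, restricting only the study-device side would create a mismatch.
- *That up to 3 months of events are certain to be included.* The 3 months is a visit window, not a stated interval from consent to surgery, and nothing shows that a preoperative event occurred.
- *That events in people never implanted enter the rates.* Section 9.4.4 excludes them.
- *That retrospective cases can contribute no preoperative event.* Their consent comes after surgery, but the chart review of operative-site events has no stated start date. This favours one onset rule for both cohorts.

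**Conclusion.** The point holds as a defect in the analysis rule. As written, the rates compared with literature on events after UKA would include any reportable event between consent and surgery in a prospective subject later implanted and kept in the safety population.

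The expected effect is small. It rests on at most about 20 case-years, which assumes that all 80 cases waited the full 3 months and that none waited longer. The increment of 0.57 points (or 1.25 points over 80) treats the unit as a case; where a row is reported per patient, the denominator differs. Under the assumed event rates the total is between a fraction of one event and a few, over all categories. The point matters mainly for the few non-implant rows that have a Table I comparator. It gives no ground for saying that the safety conclusion would change.

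**What to change.** Add to section 9.2.2 that adverse event rates, their exact 95% intervals and the comparison with the literature use events with onset at or after the start of surgery (item C = Intra-Op or Post-Op) in both cohorts, and that Pre-Op events are listed separately outside the rates.

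For the sponsor-study column of Table II, either state the event window used in those studies or also show this study's rates with all events since consent.

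The cost is a sentence or two and a filter on a field already on the form; the event date and surgery date are also recorded and allow a check. Collection from consent is unchanged and no event is hidden. Section 3.3 dates the last prospective enrolment to January 2018, so the rule is best fixed before the safety tables are produced.

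This does not remove the other differences in event ascertainment between the cohorts, which need separate handling.
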